4.3.3 Definition of Study Day

The first day of study treatment with avatrombopag or placebo will be Study Day 1. There is no Study Day 0. The day before the first day of study treatment will be Study Day -1. If an event occurs on or after the first day of study treatment, Study Day will be calculated as (Date of Event - Date of first study treatment + 1). If the event occurs prior to the first day of study treatment, Study Day will be calculated as (Date of Event - Date of first study treatment).

4.3.4 Definition of Baseline

For data displays for the Double-Blind/Observational Period, a baseline value will be the last non-missing value taken prior to the start of study treatment in the Double-Blind Period, unless otherwise indicated. For the efficacy analyses of platelet count, baseline will be defined as the lowest platelet count collected during the qualifying period in Cycle X and prior to the first dose of study drug.

For data displays for the OLE Period, a baseline value is the last non-missing value taken prior to the start of the pre-chemotherapy IP of Cycle X+3, unless otherwise indicated. For the efficacy analyses of platelet count, baseline will be defined as the lowest platelet count collected during Cycle X+2 and prior to the pre-chemotherapy IP of Cycle X+3.

Confidential

For data displays for the entire study (avatrombopag group only), a baseline value will be the last non-missing value taken prior to the start of study treatment in the Double-Blind Period, unless otherwise indicated. For the efficacy analyses of platelet count, baseline will be defined as the lowest platelet count collected during the qualifying period in Cycle X and prior to the first dose of study drug.

4.3.5 Handling Missing Data

Every effort should be made during the conduct of the study to limit the extent of missing data with subjects who prematurely discontinue IP but remain in the study for collection of data, unless the subject withdraws consent.

For efficacy summaries where the proportion of responders meeting certain criteria is calculated, data will be presented in Yes, No, and Missing categories. In the statistical testing (e.g., CMH test), subjects in the Missing category will be treated as non-responders.

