8.2 Secondary Efficacy Analysis

8.2.1 Secondary Efficacy Endpoints

The key secondary efficacy endpoints include the following:

- Duration of severe thrombocytopenia defined as a platelet count $< 50 \times 10^9/L$ during the period after post-chemotherapy IP treatment in Cycle X+1 through Chemotherapy Day of Cycle X+2

Confidential

Duration of severe thrombocytopenia will be assessed as the total number of days with platelet count $<50 \times 10^9/L$ based on platelet counts taken from the day after the last post-chemotherapy IP in Cycle X + 1 through the Chemotherapy Day in Cycle X + 2. Platelet counts collected through the expected date of Cycle X+2 Chemotherapy Day (based on 21- or 28-day cycle length after Cycle X+1 Chemotherapy Day) or the end of study date, whichever is earliest, will be considered for this endpoint.

The days between a platelet count $<50 \times 10^9/L$ and a subsequent platelet count assessment will be assumed to show severe thrombocytopenia and contribute to the duration, and days between a platelet count $\geq 50 \times 10^9/L$ and a subsequent platelet count within Cycle X+1 will not contribute to the duration. If a scheduled platelet count assessment is missing, it will be considered that the platelet count was $<50 \times 10^9/L$ at that visit.

- Change in platelet count from baseline (qualifying chemotherapy cycle [Cycle X]) (nadir) to Cycle X + 1 (nadir)

Change in platelet count from baseline is the difference between the lowest platelet value prior to the first dose of study treatment and the lowest value during Cycle X+1 (i.e., the lowest platelet value during the day after the last post-chemotherapy IP dose in Cycle X + 1 through the Chemotherapy Day of Cycle X + 2).

Multiple imputation methods using a "jump to control" procedure will be implemented to address missing Cycle X+1 (nadir). In this procedure, multiply imputed datasets will be produced using SAS PROC MI which assume that the subjects with missing Cycle X+1 (nadir) have platelet counts following a similar pattern of those subjects receiving placebo. The multiply imputed datasets are then combined using SAS PROC MIANALYZE to create a p-value for the assessment of the difference between avatrombopag and placebo groups in the mean change in platelet count from baseline. This p-value will be used in the hierarchical testing strategy defined in Section 8.2.2.

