8.3 Other Efficacy Analysis

The other efficacy endpoints include the following during the period after post-chemotherapy IP treatment in Cycle X+1 through Chemotherapy Day of Cycle X+2:

- Proportion of subjects who do not have a chemotherapy dose reduction that is $\geq 15\%$ due to thrombocytopenia;
- Proportion of subjects who do not have a chemotherapy delay that is ≥ 4 days due to thrombocytopenia;
- Proportion of subjects with a pre-defined post-baseline nadir platelet count (i.e., subjects with the lowest platelet count <10 , <25 , <50 , <75 , <100 , and $\geq 100 \times 10^9/L$ at any time);
- Proportion of subjects achieving a pre-defined post-baseline maximum platelet count (i.e., subjects with the highest platelet count ≤ 400 , >400 , and $>600 \times 10^9/L$ at any time).

Confidential

Categorical variables (eg, proportion) will be summarized and analyzed in the similar manner as the primary efficacy endpoint. If the data is sparse where the approximative methods cannot be applied, the Fisher's Exact test will be used instead.

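### For the low-nadir and high-maximum platelet categories, the Missing = non-responder rule tests subjects without counts as having the good outcome, and complementary categories then disagree

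*SAP*

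**What the plan says.** SAP 4.3.5 sets the general rule. "For efficacy summaries where the proportion of responders meeting certain criteria is calculated, data will be presented in Yes, No, and Missing categories". It then says that in testing, with the CMH test as the example, "subjects in the Missing category will be treated as non-responders". A responder is thus someone who meets the stated criteria, and no exception is made for criteria that describe harm.

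SAP 8.3 lists two platelet proportions for the period from the end of post-chemotherapy IP in Cycle X+1 to Chemotherapy Day of Cycle X+2:

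- The nadir item reads "Proportion of subjects with a pre-defined post-baseline nadir platelet count (i.e., subjects with the lowest platelet count", followed by <10, <25, <50, <75, <100 and ≥100.
- The maximum item reads "Proportion of subjects achieving a pre-defined post-baseline maximum platelet count (i.e., subjects with the highest platelet count", followed by ≤400, >400 and >600.

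On method, 8.3 says only that categorical variables "will be summarized and analyzed in the similar manner as the primary efficacy endpoint", with Fisher's exact test if data are sparse. It has no missing-data rule of its own. For the primary endpoint (SAP 8.1), missing information makes the subject a non-responder.

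SAP 8.2.1 handles the key secondary endpoints one by one. Missing bleeding data count as a bleed, and missing transfusion data count as a transfusion. For the duration endpoint, "If a scheduled platelet count assessment is missing, it will be considered that the platelet count was" below 50. For the nadir change, a missing Cycle X+1 nadir is imputed as if the subject were on placebo.

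**The concern.** Missing = non-responder is conservative only when responding is good. That holds for the primary endpoint and for the bleeding, transfusion, dose-reduction and delay proportions, all of which are worded as avoiding the event. It fails for a nadir below a cut or a maximum above one. The documents treat both as unwanted: <50 is the SAP's definition of severe thrombocytopenia, and a count >400 triggers a temporary stop of IP (SAP 3.2.1).

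If the arms differ in the number of subjects without counts, the tests can show a difference produced by the coding alone. The reader also gets two different tests of one question when complementary categories are analysed.

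**Working it through.** **Plan's own figures.** The documents give no expected rate or missingness for the nadir or maximum categories. The only sized quantity is N = 120, for the primary endpoint. The pooled two-proportion formula with continuity correction (10% vs 40%, 2:1, two-sided 0.05, 90% power) gives 36.46 placebo subjects. Then 3 × 36.46 = 109.4, and 109.4/0.9 = 121.5, close to 120. Nothing below changes that.

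**Direction of the rule.**

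| Category | Meeting it is | Missing tested as | Effect |
|---|---|---|---|
| Nadir <10, <25, <50, <75, <100 | bad | not met | scored as good |
| Nadir ≥100 | good | not met | scored as bad |
| Maximum ≤400 | good | not met | scored as bad |
| Maximum >400, >600 | bad | not met | scored as good |

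**Size of the shift (inputs assumed).** Let q be the proportion with nadir <50 among subjects with counts, and m the proportion with no count. The tested proportion is q(1 − m).

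- Equal missingness, m = 10% in both arms: 0.5 × 0.90 = 45.0% and 0.7 × 0.90 = 63.0%. Each arm is 5 to 7 points below q, and the difference between arms stays zero.
- m = 15% vs 5%, no true effect, q = 50%: 0.5 × 0.85 = 42.5% vs 0.5 × 0.95 = 47.5%, a difference of −5.0 points.
- The same with q = 70%: 0.7 × 0.85 = 59.5% vs 0.7 × 0.95 = 66.5%, a difference of −7.0 points.

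In general the artefact is −q(m₁ − m₂). It favours the arm with more missing data and changes sign when the split is reversed.

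**Whole-number check, 80 vs 40 subjects, q = 50% in both arms.**

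| Missing (active, placebo) | Rule as written | Missing = unfavourable | Observed cases |
|---|---|---|---|
| 8, 4 | 36/80 vs 18/40, 0 points | 44/80 vs 22/40, 0 points | 0 |
| 12, 0 | 34/80 vs 20/40, −7.5 points | 46/80 vs 20/40, +7.5 points | 0 |
| 4, 8 | 38/80 vs 16/40, +7.5 points | 42/80 vs 24/40, −7.5 points | 0 |

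None of these differences is significant (p = 0.436 for each 7.5-point difference). In the last two rows, changing the coding moves the estimate by 15 points and reverses its sign. Unfavourable coding is therefore not neutral either.

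**Complementary categories.** In each arm the tested proportions for <100 and ≥100 add to 1 − m, not 1. The two between-arm differences therefore add to −(m₁ − m₂), when true complements would add to zero. At 15% vs 5% the discrepancy is 10 points. Even with equal missingness the p-values differ. With 8/80 and 4/40 missing (assumed counts, unstratified Pearson chi-square):

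- Example A: <100 is 40/80 vs 30/40, p = 0.0088; ≥100 is 32/80 vs 6/40, p = 0.0055.
- Example B: <100 is 54/80 vs 32/40, p = 0.152; ≥100 is 18/80 vs 4/40, p = 0.095; observed cases, 54/72 vs 32/36, p = 0.091.

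**Against the other rules.** A subject with no in-window count is taken as <50 at each missed scheduled visit for the duration endpoint, is imputed as placebo-like for the nadir change, and is tested as not <50 in 8.3.

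**The case against.** The strongest reply is that the SAP never defines a responder for the nadir and maximum items. They are proportions of subjects, and 8.3 asks for an analysis similar to the primary, which leaves room for judgement. Where the SAP spells out missing-data handling for a proportion, it is always unfavourable, so the sponsor may have meant that here too. Coding by direction would also restore the complements. But 4.3.5 ties response to meeting the criteria and states no direction, so this intention has to be supplied by the reader.

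Several limits stand in full:

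- Summaries show Missing separately, so only the tests are affected.
- Both scheduled and unscheduled counts feed the nadir (SAP 4.1.2), and local counts are scheduled at Visits 6 to 9. A subject is Missing only if all are absent, so numbers may be small. The plan's 10% premature termination rate is not an estimate of this.
- In each complement example, both p-values fall on the same side of 0.05.

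A reader might infer three stronger things that the documents do not support. The first is that the rule favours avatrombopag; its direction depends only on which arm has more subjects without counts. The second is that every proportion endpoint is affected; those worded as avoiding an event are scored conservatively. The third is that any missed visit sets 8.3 against the duration endpoint. That rule fills single visits, whereas one available count is enough to derive a nadir, so the rules collide only for subjects with no in-window count.

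**Conclusion.** The concern holds in this limited form. As written, SAP 4.3.5 and 8.3 together test subjects without in-window local counts as having the good outcome on seven categories (five nadir, two maximum) and as failing both members of two complementary pairs. This runs against the unfavourable scoring that the SAP states for bleeding, transfusion and missed scheduled counts.

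Under the assumed rates and missingness the artefact is 5–7 points. It is zero when missingness is equal and reverses with the split. The p-values are unstratified illustrations, not the planned CMH test. No confirmatory conclusion depends on these endpoints, which lie outside the four-step hierarchy in SAP 8.2.2. This is a minor correction worth making.

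**What to change.** Before database lock and unblinding:

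- **SAP 4.3.5:** limit Missing = non-responder to endpoints whose criterion is the favourable outcome.
- **SAP 8.3, nadir:** state and test the categories as ≥10, ≥25, ≥50, ≥75 and ≥100, with missing as not met. Add an observed-case analysis, as SAP 8.4 already plans for the primary endpoint.
- **SAP 8.3, maximum:** for ≤400, >400 and >600, state as an explicit exception to 4.3.5 that the denominator is subjects with at least one in-window count. Report the number missing by arm.

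The cost is SAP wording and one extra analysis of data already planned; no new data are needed. Low-nadir results become slightly less favourable. Scoring missing as not met penalises the arm with more missing data and is severe at the lowest cut, where a subject with no data counts as below 10. The observed-case analysis shows how far the result depends on that choice.

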4.3.6 Partial Dates

For the purpose of inclusion of appropriate data records in the analysis, some partially missing dates will have date imputation performed. However, these imputations will be limited to table summaries; listings will retain the date as entered in the database. The following imputations will be performed:

Time since Primary Cancer Diagnosis: Prior to calculating this variable, missing month and day will be set to June 15th. If only day is missing, the day will be set to the 15th of the month. If a date is completely missing, no imputation will be performed.

Medications:

- If a start date is missing the day
 - Set to the 1st of the month
- If a start date is missing the day and month
 - Set to January 1st if study treatment began the year prior to the year of medication start
 - Set to January 1st if the medication is known to start in a year prior to study treatment
 - If the medication and the study treatment start the same year, the medication start date will be set to the study treatment start date.
- No medication end dates will be imputed
- No completely missing dates will be imputed. If, after imputation, it cannot be determined whether a medication was taken prior or concomitantly, it will be considered a concomitant medication.

In general, the assumptions about the missing or partially missing dates, when needed, are made conservative to avoid overestimation of treatment effect and underestimation of adverse effects.

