4.2.2 Per-Protocol Analysis Set (PPS)

The PPS will include the subset of subjects from the FAS who do not meet the criteria that would potentially impact the evaluation of the efficacy endpoints. A full list of the criteria will be finalized prior to database lock and unblinding. Examples of these criteria may include:

- Use of certain prohibited concomitant medications
- Selected Inclusion/Exclusion criteria not met for the Double-Blind period

Confidential

- Lack of compliance with study medication during the Double-Blind period
- Study Discontinuation resulting in an inability to assess the primary efficacy endpoint
- Assigned to incorrect treatment (mis-randomization) or receiving incorrect study medication

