6.3 Oncology History

Descriptive statistics with respect to oncology history and cancer characteristics will be displayed by treatment group for the FAS. The variables to be summarized are:

Confidential

- Primary Cancer Diagnosis: Ovarian, Non-small cell lung cancer, Small cell lung cancer, Bladder cancer
- Stage (I, II, III, IV)
- Time since diagnosis (years), defined as (Date of randomization – Date of Diagnosis)/365.25
- Cycle length of current regimen: 21-day or 28-day
- Cycle of Chemotherapy at Study Entry, both continuous and categorical
- Prior Surgery for Current Cancer (Yes/No)
- Prior Radiation for Current Cancer (Yes/No)
- Prior Chemotherapeutic Regimens for Current Cancer (Yes/No) and number of prior chemotherapy regimens (1 or 2)
- Number of Eligible Chemotherapy Agents recorded on eCRF (1, 2, 3, or 4)

A listing of oncology history will be provided.

7. Prior and Concomitant Treatment

Prior and Concomitant medications will be classified according to the World Health Organization (WHO) Drug Dictionary (March 2020, B3). The coding version may be updated prior to database lock if a newer version is available. Medications will be coded per the Anatomical Therapeutic Classification (ATC). All medications will be documented from the time of informed consent up to the Follow-up visit.

Prior medications are those which start and stop before the first day of study treatment in the Double-Blind period. Concomitant medications for the Double-Blind/Observational period are those which start on or after the first day of study treatment and prior to the first dose of the study drug in the OLE period. A medication which begins before the start of study treatment in the Double-Blind period and continues into the Double-Blind period will be considered as concomitant for the Double-Blind/Observational period.

Concomitant medications for the OLE period are those which begin prior to the OLE period and continue into the OLE period or those which start on or after the first day of study treatment in the OLE period.

Tabular summaries will display the number and percentage of subjects with at least one medication in ATC Level 2 and preferred term categories and overall. Subjects who have taken a medication more than once will only be summarized once per ATC Level 2 or preferred term.

The tabular summaries to be provided are as follows:

- Prior Medications
- Concomitant Medications (Double-Blind/Observational period)
- Concomitant Medications (OLE period)

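### The same-year rule for year-only medication starts (SAP 4.3.6) ignores a recorded stop before the first dose, so a drug already stopped is counted as concomitant

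*SAP*

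**What the plan says.** SAP 4.3.6 (Partial Dates) sets the medication rules by what is missing. A start lacking only the day goes to the first of the month. The branch at issue begins "If a start date is missing the day and month" and has two outcomes. A start in an earlier year than study treatment goes to 1 January of that year. For a start in the treatment year, "If the medication and the study treatment start the same year, the medication start date will be set to the study treatment start date". On stops, the section says only "No medication end dates will be imputed". It closes with a fallback: "If, after imputation, it cannot be determined whether a medication was taken prior or concomitantly, it will be considered a concomitant medication". Its scope is stated at the outset: "these imputations will be limited to table summaries; listings will retain the date as entered in the database".

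SAP Section 7 (Prior and Concomitant Treatment) supplies the classification: "Prior medications are those which start and stop before the first day of study treatment in the Double-Blind period". A medication starting on or after the first study treatment day, and before any open-label dose, is concomitant for the Double-Blind/Observational period. That limb has no stop-date condition. Medications are documented from informed consent onward.

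For the date of primary cancer diagnosis, SAP 4.3.6 says that "missing month and day will be set to June 15th", and a missing day becomes the 15th. SAP 6.3 computes time since diagnosis as randomization date minus diagnosis date, divided by 365.25.

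**The concern.** An imputed date should not contradict a date that was actually recorded. The same-year branch looks only at the year of the start, so it can place the start after a known stop. Section 7 then tests the imputed start, and a drug that had ended before any study treatment is tabulated as taken alongside it.

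What is at stake is the accuracy of the prior and concomitant medication tables. Those tables describe what subjects were taking while on study drug, so a drug stopped in screening does not belong in the concomitant one. The diagnosis rule has a similar gap: nothing prevents an imputed diagnosis date from falling after randomization.

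**Working it through.** The plan states no figure on this point, so the check is to apply its rules literally.

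**Inputs**
- Imputation rules: SAP 4.3.6.
- Prior and concomitant definitions, and collection from consent: SAP Section 7.
- Screening up to 28 days before Baseline: SAP 3.2. Baseline may fall one day before the first dose: Protocol 6.2.2.
- First dose on 15 June 2020: an assumption for illustration only.

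**Single records, first dose 15 June 2020**

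| Recorded start | Recorded stop | Imputed start | Class | Start after stop? |
|---|---|---|---|---|
| 2020 | 10 June 2020 | 15 June 2020 | concomitant | yes, by 5 days |
| 2020 | 14 June 2020 | 15 June 2020 | concomitant | yes, by 1 day |
| 2020 | 1 July 2020 | 15 June 2020 | concomitant | no |
| 2020 | missing | 15 June 2020 | concomitant | no |
| June 2020 | 10 June 2020 | 1 June 2020 | prior | no |
| 2019 | 10 June 2020 | 1 January 2019 | prior | no |

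The fault therefore sits in one branch only: a year-only start in the treatment year with a known stop before the first dose.

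**Every possible stop in that branch.** From 1 January to 14 June 2020 there are 31 + 29 + 31 + 30 + 31 + 14 = 166 dates. All 166 give a start after the stop and a concomitant class. The reason is general: the imputed start equals the first dose date, so it always fails the prior definition and always meets the concomitant one.

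**Can it arise?** Yes. The 28-day screening window plus the one-day Baseline offset gives 29 days before the first dose in which a stop can fall after consent. All 29 stop dates fail in the same way. Where Screening and Baseline are combined the day before dosing, the window is almost nil.

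**With a stop-date condition.** Using the earlier of first dose and recorded stop, each of the 166 records takes its stop date as its start. The start is then never after the stop, both precede the first dose, and all 166 are prior. Records with a missing stop, or a stop on or after the first dose, do not change.

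**Diagnosis date.** Take a diagnosis recorded as 2019 and randomization on 1 April 2019. The imputed diagnosis is 15 June 2019. Time since diagnosis = (1 April − 15 June)/365.25 = −75/365.25 = −0.21 years. The true value must lie between 0 and 90/365.25 = 0.25 years, since 1 January to 1 April 2019 is 90 days. The fault needs a year-only diagnosis in the same year as a randomization before 15 June.

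**The case against.** The best defence is that 4.3.6 declares its date assumptions conservative and sends unresolved cases to concomitant, so any error runs in a chosen direction. That is reasonable where information is missing. It does not cover this case, because a recorded stop before the first dose already settles the classification.

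A second defence is scope. Imputation applies to tables only, and listings keep the dates as entered, so the impossible order of dates appears only in derived data and no table prints it. That stands, but the misclassification occurs in exactly those tables. Section 7 also has the medication listing flag each record as prior or concomitant. If that flag follows the table classification, which the SAP does not say, the listing would show concomitant beside a stop before dosing.

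A third defence is size, and it largely stands. The tables count a subject once per ATC Level 2 class or preferred term, so a count changes only when no other record of that subject qualifies in the same category. Time since diagnosis is purely descriptive. Diagnosis date is specifically collected (Protocol Appendix A, Table 1), and missing data are queried (Protocol 11.1.5).

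Two stronger readings are tempting, and the documents support neither.
- A reader might infer that misclassified drugs could remove subjects from the Per-Protocol Set, because SAP 4.2.2 mentions "Use of certain prohibited concomitant medications". That entry is only an example in a list still to be finalized. Imputed dates are confined to table summaries, and nothing says that membership is read from the imputed classification.
- A reader might infer that long-term medication is the main casualty. A drug begun in an earlier year takes the 1 January branch, which works correctly, and a drug still in use at the first dose is properly concomitant.

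**Conclusion.** The same-year rule is wrong as written. For every medication with a year-only start in the treatment year and a known stop before the first dose, it produces a start after the stop and the wrong class. These are mainly drugs stopped during screening.

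The importance is low. The effect is a probably small overcount in the descriptive concomitant medication tables and an equal undercount in the prior medication table. The number of affected records is not given, so the size cannot be stated more closely. The primary endpoint, the testing hierarchy and the sample size do not use this rule.

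The conclusion rests on reading 4.3.6 and Section 7 literally. A programmer might add a stop-date check unprompted, but the plan does not ask for one. The negative time since diagnosis is a minor side point of the same kind.

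**What to change.** Replace the same-year branch in SAP 4.3.6 with wording such as:

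> *Where a year-only start falls in the year of the first study dose, impute the earlier of the first dose date and the recorded stop date. A medication whose recorded stop precedes the first dose is prior.*

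The second sentence settles the class without imputing any end date, so the existing rule on end dates can stay.

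For time since diagnosis, add that an imputed diagnosis date (June 15 or the 15th of the month) may not be later than the date of randomization.

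The cost is two short clauses and minor programming before database lock. No new data are needed.
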